10.2 Sample Size

Calculation of the sample size was performed with looking at the primary endpoint of total morphine usage post laparotomy. In a similar previous study the total dose of administered morphine was 62mg with a standard deviation of 16mg.⁴ As stated above it was decided that a difference of 20% (12mg) would be considered clinically relevant, similar to this previous study.

A: Assuming $\alpha = 0.05$ and $\beta = 0.15$ (a power of 85 per cent), a total of 62 patients (31 patients per group) would be required to find there was no difference between each group.¹⁰

This means that with this sample size this study has an 85% chance of finding out if there is a statistically significant ($p < 0.05$) 20% reduction in total narcotic usage until day 3 post op with surgically placed, instead of U/S guided rectus sheath catheters.

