All enrolled patient will be randomised into two even arms via random allocation sequence in numbered envelopes. A third party doctor using computer randomisation will conduct the randomisation prior to commencement of the project. The allocation will be revealed prior to closure of the abdomen where the patient will either receive a surgically placed pre-peritoneal catheter or an ultrasound guided rectus sheath catheter inserted by the anaesthetic team prior to waking up from the general anaesthetic.

These catheters will then be intermittently infused with local anaesthetic over the next 72 hours via a pump. Over this time the patients' opiate analgesic requirement and the visual analogue scale (VAS) will be monitored daily. The surgical team and the anaesthetic pain team will review the patients daily for the above and monitor for adverse effects from the procedure/local anaesthetic.

Eligibility Criteria (Inclusion and Exclusion)

Inclusion: All adult general surgical patients undergoing a midline laparotomy at Mackay base hospital

Exclusion Criteria:

- Local Anaesthetic allergy
- Catheter plastic allergy
- Multiple operations as defined as alteration of anatomy of the abdominal wall, preventing placement of catheters.
- Chronic abdominal pain as defined as abdominal pain with opiate use for > 12 weeks
- Abdomen left open
- Patient under 18 years of age
- Pregnant
- Inability of surgical/anaesthetic staff to perform procedure
- Patients with altered cognition (dementia or delirium) and therefore unable to respond to

VAS.

- Patients intubated & therefore unable to communicate

Sample Size Determination:

Calculation of the sample size was performed by using the primary endpoint of 72-hour total morphine usage post laparotomy. In a similar previous study, the total dose of administered morphine was 62mg with a standard deviation of 16mg.⁴ It was decided that a difference of 20% (12mg) would be considered clinically relevant, similar to this previous study.

Assuming $\alpha = 0.05$ and $\beta = 0.15$ (a power of 85 per cent), a total of 66 patients (33 patients per group) would be required to find there was no difference between each group¹⁰. Assuming a 10% dropout rate 72 patients need to be recruited (36 patients per group) to make this number.

2 Introduction

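### The synopsis requires 66 patients and section 10.2 requires 62 from the same printed inputs, and 72 less 10% does not leave 66; the effect on power is small

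*Protocol*

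**What the plan says.** The sample size is justified twice in the protocol: in the synopsis under Sample Size Determination, and in section 10.2. Both take from one earlier study that "the total dose of administered morphine was 62mg with a standard deviation of 16mg", both adopt "a difference of 20% (12mg) would be considered clinically relevant", and both set alpha at 0.05 and "a power of 85 per cent".

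The conclusions differ. The synopsis states "a total of 66 patients (33 patients per group) would be required"; section 10.2 states "a total of 62 patients (31 patients per group) would be required".

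The synopsis then adds "Assuming a 10% dropout rate 72 patients need to be recruited (36 patients per group) to make this number", where the number to be made is 66. Section 10.2 mentions neither dropout nor 72. It says instead that its sample size gives an "85% chance of finding out if there is a statistically significant" reduction of 20% in narcotic use to day 3. Section 5.1 and the participant line of the synopsis both put recruitment at 72, with section 5.1 giving 36 per arm.

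**The concern.** One set of inputs cannot require both 66 and 62 patients, so at least one section does not follow from what it prints. The dropout allowance also does not do what the synopsis says it does.

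The required number of analysable patients is the yardstick against which the finished trial will be judged. Section 10.3 lets patients with missing or implausible results be left out of the analysis, so the analysed number may well fall below 72. If it ends between 62 and 65, the trial has reached its target by section 10.2 and missed it by the synopsis. A published report would inherit the same ambiguity.

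**Working it through.** **Inputs.** From the synopsis and section 10.2: reference mean 62 mg, SD 16 mg, difference printed as 20% and as 12 mg, alpha 0.05, power 85%. Equal arms come from the study design. Sidedness and the exact test are not stated; I assume a two-sided comparison of two means. Taken literally, 20% of 62 mg is 0.20 × 62 = 12.4 mg, while 12 mg is 12/62 = 19.4%.

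**Required number per group.** The normal approximation is n = 2 × [SD × (z for 0.975 + z for 0.85) / difference]². The t-test value solves the corresponding noncentral-t power equation.

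| Difference | Normal approximation | t-test | Protocol figure matched |
|---|---|---|---|
| 12 mg | 31.92, so 32 (64 in total) | 32.91, so 33 (66 in total) | Synopsis, by the t-test |
| 12.4 mg | 29.90, so 30 (60 in total) | 30.89, so 31 (62 in total) | Section 10.2, by the t-test |

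Both figures are reproduced exactly by one method, the two-sided t-test, with two different effect sizes. A one-sided normal calculation at 85% power gives 52 in total for 12 mg and 48 for 12.4 mg, and so matches neither. A one-sided normal calculation for 12 mg also lands on 62, but only at 90% power, which the protocol does not state. The 12 versus 12.4 mg explanation is therefore the natural one, but it remains an inference.

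**Power for the numbers in play.**

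| Analysed per group | 12 mg, t-test | 12 mg, normal | 12.4 mg, t-test | 12.4 mg, normal |
|---|---|---|---|---|
| 31 (62 in total) | 82.8% | 84.0% | 85.1% | 86.2% |
| 32 (64 in total) | 84.0% | 85.1% | 86.3% | 87.3% |
| 32.4 (64.8 in total) | 84.4% | 85.5% | 86.7% | 87.7% |
| 33 (66 in total) | 85.1% | 86.1% | 87.3% | 88.3% |
| 36 (72 in total) | 88.1% | 88.9% | 90.0% | 90.8% |

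**Dropout.** To keep N after a fraction d is lost, recruit N / (1 − d).

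- For 66: 66 / 0.9 = 73.3, so 74 (37 per group).
- What 72 leaves after 10% loss: 72 × 0.9 = 64.8, below 66.
- Loss that 72 can absorb while keeping 66: 6 / 72 = 8.3%.
- Possible origin of 72: 66 × 1.1 = 72.6, rounded down. This too is inferred.
- For 62: 62 / 0.9 = 68.9, so 69, and 72 is enough.

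**The case against.** A reader might infer from these slips that the trial does not deliver its stated 85% power. The documents do not support that. Recruitment is 72 wherever it is stated, and nowhere does the protocol plan to recruit 62. After the full 10% loss, power for 12 mg is 84.4% by the t-test and 85.5% by the normal approximation; for 12.4 mg it is above 85% by either method. At worst the shortfall is under one point, or one point if the analysed total is rounded down to 64. That is small beside the uncertainty of an SD taken from a single earlier study of different catheter placements.

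A reader might also infer that the power sentence in section 10.2 is false. It is not, on its own wording: it speaks of a 20% reduction, the 62 mg base is printed beside it, and 31 per group gives 85.1% for 12.4 mg. The 82.8% in the table arises only if the 12 mg printed in the same section is taken literally and only 62 patients are analysed, which would mean losing 10 of 72, or 13.9%.

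Both objections stand, and they limit the point to consistency. They do not remove it: the two sections still require different numbers from identical printed inputs, and 72 less 10% is still not 66.

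**Conclusion.** Wrong as written, but minor. The required number differs by four patients between the synopsis and section 10.2, most probably because 20% was entered as 12 mg in one calculation and as 12.4 mg in the other. The dropout inflation in the synopsis is two patients short of what it claims (72 against 74) and covers 8.3% loss rather than 10%. Measured against the 62 of section 10.2 there is no dropout shortfall at all. Power for the trial as planned stays within about one point of 85%, or above it.

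These results assume a two-sided 5% test, equal arms and an SD of 16 mg. The explanation for the two totals rests on the exact match of both to the t-test calculation; the protocol does not state it.

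**What to change.** Keep recruitment at 72. In both the synopsis and section 10.2, state one difference in mg, the test and its sidedness, one required number and one dropout statement. Either of these is coherent:

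- **12 mg.** Required: 66 (33 per group), two-sided t-test, 85% power. Say that 72 allows for about 8% loss, or that 10% loss leaves about 64 patients and about 84% power. Remove 62 and 31 from section 10.2, and express its power sentence as a 12 mg reduction.
- **12.4 mg (exactly 20% of 62 mg).** Required: 62 (31 per group), two-sided t-test, 85% power. Allowing for 10% loss this needs 69, so 72 is enough. Remove 66 and 33 from the synopsis, and replace the printed 12 mg in both places.

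The choice should follow from which difference the investigators meant as clinically relevant. The cost is wording only: no extra patients and no change to the design or the analysis. Under the first option with 10% loss, the stated power becomes about one point less favourable.

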10.3 Statistical Analysis

All analysis will be performed by a qualified statistician at TTH. The first analysis will be to investigate if there are any significant difference between the demographics and primary clinical characteristics of each arm using Student's *t*-test or Fisher's exact test as appropriate.

Repeated measurements (pain scores) will be analysed by repeated measures ANOVA or ANOVA on ranks, with further paired comparisons at each time interval performed using the *t*-test or Mann–Whitney *U*-test as appropriate. Categorical data will be analysed using χ^2 analysis or Fisher's exact test where applicable. Normally distributed data such as morphine usage will be presented as means \pm sd of the mean, non-normally distributed data are presented as medians \pm quartiles (interquartile range), and categorical data are presented as raw data and as frequencies. Other testing may be done at the statistician's discretion.

The α level for all analyses was set as $P < 0.05$. The endpoints will then be analysed for any statistically significant differences. The arms will not be broken down further by demographics or primary clinical characteristics due to the small size likely causing spurious results.

If there is a false reading (eg morphine usage of 600mg instead of what was likely 60mg); the data and collection tools will be audited again. If the discrepancy cannot be found the patient result may be left out of the analysis, but will be clearly outlined that they were excluded and why in the report. Similarly, if there is missing information, the patient's result may be left out of the analysis, but will be clearly outlined why they were excluded in the report.

11 Data Management

The data collection sheets as well as the patient's electronic notes will be used to collect the data at first. Once a full data set for the patient is complete (Minimum of 2 months post procedure to record any late complications in the follow up), the data will then be completely de-identified and placed on a password protected excel spreadsheet. This will be audited by an independent surgical registrar. Once this is audited, the data collection tool and any re-identifiable materials will be disposed in confidential waste bins. This password protected completely de-identified spreadsheet will be kept on a private QH drive and the investigators personal drive to ensure 2 copies. This data will be kept for the minimum 15 years required.

12 Monitoring and Quality Assurance

Monitoring will occur via the three surgical doctors co-authoring this study in Mackay. They will be observing that the study is going as per protocol with recruitment, allocation and data collection. They will have routine meetings with the surgical and anaesthetic staff involved to ensure proper recruitment and protocol adherence.

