5.1 Number of participants

72 patients (36 patients per arm)

The following demographics and primary clinical characteristics which may cause a difference between the arms are outlined below. These will be record and analysed between the 2 arms to ensure there is nil significant bias.

Demographic factors

- Sex
- Age
- BMI
- ASA Score
- Creatnine

Primary clinical characteristics

- Procedure
- Procedure time
- Incision type (Full midline, upper midline, lower midline)
- Incision Length
- Stoma
- HDU/ICU Requirement
- Anaesthetic used

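### Significance tests on 12 characteristics cannot show that the arms are free of bias, and the list mixes pre-allocation variables with two whose timing is undefined

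*Protocol*

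**What the plan says.** Protocol section 5.1 introduces its list with "The following demographics and primary clinical characteristics which may cause a difference between the arms are outlined below" and states the purpose of collecting it: "These will be record and analysed between the 2 arms to ensure there is nil significant bias". The list has five demographic factors (sex, age, BMI, ASA score, creatinine) and seven clinical characteristics (procedure, procedure time, incision type, incision length, stoma, HDU/ICU requirement, anaesthetic used).

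Section 10.3 turns this into the first step of the analysis: "The first analysis will be to investigate if there are any significant difference between the demographics and primary clinical characteristics of each arm". The tests are Student's t or Fisher's exact. The 0.05 threshold covers them too, because the "level for all analyses was set as" wording makes no exception for baseline comparisons. Nothing says what follows if a characteristic differs significantly.

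On the timing of randomisation, the Synopsis (Study Design) says "The allocation will be revealed prior to closure of the abdomen". Section 7.4 places the surgical catheter before wall closure and the ultrasound catheter after it. Section 5.1 lists "HDU/ICU Requirement" and "Procedure time" without saying when either is measured.

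On the use of these variables in the endpoint analysis, section 10.3 says only "The arms will not be broken down further by demographics or primary clinical characteristics due to the small size". It describes how morphine use will be presented, names no covariate model, and leaves further tests to the statistician.

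**The concern.** Allocation is computer-generated and concealed (sections 4 and 7.5). If that works, any difference between the randomised arms in a variable fixed before allocation is chance by construction. Testing it asks a question whose answer is already known. The p-value measures neither bias nor how far an imbalance could distort the comparison of opioid use.

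The check can therefore mislead in two ways. A chance result may be reported as a failure of randomisation and, with further testing left open, may prompt an adjustment chosen after seeing the data. Or a set of non-significant results may be taken as proof of comparability, although the tests have little power at this sample size.

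The mixed list adds a third problem. If HDU/ICU requirement is recorded after surgery, or procedure time runs to closure or to the end of theatre, a difference between arms could be an effect of the catheter technique. Read as a baseline check, it would be taken for bias.

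Finally, the proper use of prognostic variables is to pre-specify a few of them in the model for the primary endpoint. The protocol gives its effort to the tests and is silent on that use.

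**Working it through.** **The plan's own figure.** The protocol gives no error rate for the baseline tests. Its sample size inputs (section 10.2) are a difference of 12 mg, SD 16 mg, alpha 0.05 and power 85%. Taking the test as two-sided,

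n per arm = 2 × 16² × (1.960 + 1.036)² / 12² = 31.9, rounded up to 32.

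Section 10.2 states 31 per group and the Synopsis 33. These two figures should be reconciled, but that is a separate matter. I use 32 per arm for power and the Synopsis figure of 33 for the imbalance example.

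**Chance of a false signal.** There are 5 + 7 = 12 variables, each tested at 0.05.

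| Assumption | P(at least one p < 0.05) |
|---|---|
| 12 independent tests: 1 − 0.95¹² | 46.0% |
| Common correlation 0.1 (simulated) | 45% |
| Common correlation 0.3 (simulated) | 40% |
| Common correlation 0.5 (simulated) | 32% |
| 5 tests at 0.05, 7 binary by Fisher's exact test (true size about 0.025 to 0.028 at 36 per arm) | 35 to 36% |
| Without HDU/ICU requirement and procedure time: 1 − 0.95¹⁰ | 40.1% |

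The expected number of false signals is 12 × 0.05 = 0.6 if every test has its nominal size. The correlations are assumptions; the protocol gives none.

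**What a non-significant result can hide.** Take a covariate that differs by 0.4 SD between arms of 33. Then t = 0.4 / √(2/33) = 1.62 on 64 degrees of freedom, so p = 0.11 and the variable passes. If that covariate explains a share R² of the variance in opioid use, the shift in the arm difference is 0.4 × √R² × 16 mg:

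- R² = 0.1: 2.0 mg, which is 17% of the 12 mg target
- R² = 0.2: 2.9 mg, which is 24% of the 12 mg target

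**Timing.** The envelope is opened just before closure. Age, sex and BMI are fixed by then, and incision type, incision length and stoma should be. HDU/ICU requirement could be a pre-operative plan or a post-operative fact. Procedure time could stop before or after the catheter step, and that step comes at a different point in the two arms. Section 5.1 does not say which is meant.

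**What adjustment could give.** Adjusting for covariates multiplies the residual SD by √(1 − R²). Two-sided t-test power (non-central t) at 32 per arm and 12 mg:

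| R² (assumed) | Residual SD | Power |
|---|---|---|
| 0 | 16.0 | 84.0% |
| 0.1 | 15.2 | 87.6% |
| 0.2 | 14.3 | 91.0% |

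These figures ignore the cost of estimating the covariate effects. For k covariates and N = 64, the expected loss from chance imbalance inflates the variance by 1 + k/(N − k − 3), and k degrees of freedom are lost. With k = 2 the factor is 1 + 2/59 = 1.034 and power is 86.4% at R² = 0.1 and 90.1% at 0.2. With k = 4 it is 1 + 4/57 = 1.070 and power is about 85% and 89%.

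**The case against.** The strongest reply is that no analysis depends on the baseline tests. Section 10.3 attaches no adjustment, exclusion or change of model to a significant result, so the type I error of the primary comparison is untouched. That stands. The harm lies in interpretation and in the opening left for data-driven choices. It does not make the main comparison invalid.

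A reader might also infer that the plan commits itself to an unadjusted comparison and so wastes the prognostic data. The document does not support this. The t and rank tests in section 10.3 are assigned to pain scores at each time interval. For morphine use only the form of presentation is given. What is excluded is subgroup breakdown, not adjustment, and a separate analysis plan may settle the model. The most that can be said is that no adjusted analysis is named.

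Nor can HDU/ICU requirement and procedure time be called post-allocation as a fact. Either could be defined otherwise, and most of the operating time precedes the envelope. Time taken for the catheter is already a separate secondary endpoint. What stands is that the list does not separate the two kinds of variable.

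A further inference would be that emergency or elective status and pre-operative opioid use are not collected. They are absent from the section 5.1 list, but the data collection forms are attachments that are not shown, so this cannot be established.

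The 46% is the upper end. Several variables are plainly related (procedure, incision and stoma; age and ASA score), so the range is the fairer statement. Lastly, section 10.3 lets patients with missing or implausible data be left out after randomisation, so the analysed arms could differ for reasons other than chance. That is a reason to account for exclusions by arm. A baseline p-value would not identify the cause.

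**Conclusion.** The point holds in this form: the protocol fixes significance tests on 12 characteristics as its check for bias, and such tests cannot do that job. This is a wrong method written into the text, not a detail left for later. Under sound randomisation it gives at least one false signal in roughly 32 to 46% of trials, depending on the correlation among the variables and on the conservatism of Fisher's exact test. It can also pass an imbalance worth 2.0 to 2.9 mg of the 12 mg target, if the covariate explains 10 to 20% of the variance.

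That two listed variables may not be baseline is an inference from undefined timing. The gain from adjustment, from 84% to about 88 to 91% power at 32 per arm before the small cost of estimating the covariates, rests wholly on an assumed R², for which the protocol gives no figure. The primary comparison remains valid as it stands. The change is worth making because it removes a misleading step at almost no cost.

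**What to change.** 1. In section 10.3, delete the significance tests of demographics and clinical characteristics. In section 5.1, delete the stated purpose of excluding bias. Tabulate the characteristics by arm without p-values.
2. In section 5.1, mark which variables are fixed before the envelope is opened. Report HDU/ICU requirement and procedure time separately, unless they are defined as pre-allocation values.
3. Before data are seen, fix the primary analysis as a linear model of 72-hour opioid use on arm, adjusted for a short list of pre-allocation variables already collected, for example age and incision length. Give the unadjusted difference as a sensitivity analysis. The choice of covariates must not depend on observed imbalance.

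The cost is a change of wording in two sections and a few degrees of freedom. With two covariates, the worked figures lose about one percentage point of the power gain. If the covariates explained nothing, power at 32 per arm would fall slightly, from 84.0% to 82.7% by the same formula (R² = 0, k = 2).

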6.2.2 Day 1,2,3

Data collection will begin with documenting intraoperative analgesia & anaesthesia requirements. Subsequently data will be collected on the premise of the VAS 12 hours post-operatively (at rest & at coughing) by the Surgical/Anaesthetic Registrar or Consultant. On the surgical ward round the registrar or consultant will ask whether the patient has opened bowel or passed flatus. All data will be recorded on the data collection tool, which will be placed in the patient's chart. The morphine equivalent analgesia can be, but does not have to be filled in. This can be retrospectively analysed for the patient med chart, chart notes, and anaesthetic pain round by the investigators. The investigators will be directly involved in reviewing each patient recruited in this study.

At any stage any complications can be written at the bottom of the Data collection tool.

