10.1 Hypotheses

Null hypothesis: Surgically placed pre-peritoneal catheters are superior to ultrasound placed rectus sheath catheters at reducing post-operative pain.

This hypothesis will be tested by the primary endpoint of total narcotic usage until day 3 post op and Patient blinded VAS scores at rest and coughing (0-10). These are both discussed below

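### The overall across-day test of VAS pain scores can drop patients with a missing score or rests on an unidentified rank method; a mixed model on all observed scores would serve better

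*Protocol*

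**What the plan says.** For the pain scores, Protocol section 10.3 fixes the method: "Repeated measurements (pain scores) will be analysed by repeated measures ANOVA or ANOVA on ranks". The sentence goes on "with further paired comparisons at each time interval performed using the" t-test or Mann-Whitney test. It gives no rule for choosing between the ANOVA and the rank option.

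The only rule for missing information, in the same section, is that the patient's "result may be left out of the analysis, but will be clearly outlined why they were excluded in the report". The section also allows that "Other testing may be done at the statistician's discretion".

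VAS at rest and on coughing is listed as a secondary endpoint in the synopsis and in section 3. Section 10.1 gives it a larger role: "This hypothesis will be tested by the primary endpoint of total narcotic usage until day 3 post op and Patient blinded VAS scores". The schedule table in section 6.2 has VAS on days 1, 2 and 3. The text of section 6.2.2 also mentions a score at 12 hours, which may or may not be a separate time.

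**The concern.** The two named options have different faults, and neither gives a sound overall comparison of the arms across days when some scores are missing.

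- **Repeated measures ANOVA**, in its classical form, needs every score from every patient. One missed score removes the patient along with the scores that were obtained.
- **ANOVA on ranks** could mean several procedures. Some ignore the repeated structure; others respect it but do not compare the arms.

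Some missing scores are foreseeable. Patients may withdraw from further data collection (section 9.3), treatment can be discontinued early (section 9.2), and some patients will need HDU or ICU care (section 5.1). The schedule marks morphine use for recovery at chart review but not VAS, so a missed score is not planned to be recovered. If the reasons for missing scores are tied to recovery, the complete patients are a selected group.

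At stake are the precision, and possibly the validity, of the across-day result for the measure that bears most directly on the pain named in the hypothesis.

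**Working it through.** The protocol states no figure for the pain-score analysis, so there is none to reproduce. The check sizes the problem.

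**Inputs from the protocol.** 72 patients, 36 per arm (synopsis, section 5.1); alpha 0.05 (section 10.3); k = 3 score times from the schedule, or k = 4 if the 12-hour score is separate.

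**Assumed inputs, not in the protocol.** Share m of single scores missing, 2% to 10%, independent across times; within-patient correlation rho, 0.3 to 0.7.

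**1. Patients left by complete-case deletion.** The expected number complete is 72 × (1 − m)^k.

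| m | k = 3 | k = 4 |
|---|---|---|
| 2% | 72 × 0.941 = 67.8 | 72 × 0.922 = 66.4 |
| 5% | 72 × 0.857 = 61.7 | 72 × 0.815 = 58.6 |
| 10% | 72 × 0.729 = 52.5 | 72 × 0.656 = 47.2 |

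The share of observed scores thrown away is 1 − (1 − m)^(k−1). For k = 3 that is 4%, 10% and 19%.

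**2. Precision lost against an analysis of all observed scores.** This compares the variance of the three-day average arm difference under complete cases with that under a likelihood (GLS) analysis, with 36 per arm, equal correlation between days and scores missing completely at random. The ratio, over rho from 0.3 to 0.7, is:

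- m = 2%: 1.05 to 1.06
- m = 5%: 1.14 to 1.17
- m = 10%: 1.30 to 1.36

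Taking square roots, confidence intervals would be wider by about 3%, 7 to 8%, and 14 to 17%.

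**3. The rank option, by reading.**

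- *Kruskal-Wallis on all scores pooled as independent.* The true variance of the arm contrast is larger than the test assumes by about 1 + (k − 1) × rho, which for k = 3 is 1.6, 2.0 and 2.4 at rho 0.3, 0.5 and 0.7. The approximate type I error is 2 × [1 − Φ(1.96/√factor)]. That gives 1.96/1.265 = 1.55, so 0.12; 1.96/1.414 = 1.39, so 0.17; and 1.96/1.549 = 1.27, so 0.21. Simulation (4,000 runs, 36 per arm, three scores each, no true difference) gave 0.12, 0.16 and 0.21.
- *Friedman.* This respects the repeated structure, but it ranks days within patients. It therefore compares days, not arms, and needs complete data.
- *A rank test at each day separately.* The type I error per test is not inflated, but there is no overall test across days.

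**4. The per-day comparisons.** Mann-Whitney is a test for independent samples. Despite the word paired, these comparisons are most naturally arm against arm at each day, and they do not need a full set of scores.

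**The case against.** Several points on the other side stand.

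- **Per-day arm comparisons are planned.** A reader might infer that the plan has no valid comparison of pain between arms. It has one at each day; only the overall test is in question.
- **The rank method is unnamed, not shown to be wrong.** A reader might infer that it ignores the repeated structure. That follows only on the pooled Kruskal-Wallis reading; a Friedman reading respects it.
- **Deletion is permitted, not required.** The missing-data rule says may, and the discretion clause allows other tests. Both leave room for a better analysis, but neither specifies one, and both leave the choice open after the data are seen.
- **Missing scores may be few.** VAS is taken in hospital, both teams review patients in the first 72 hours (section 4), and patients with altered cognition or who are intubated are excluded (section 5.3). The protocol does not show that scores will be missing.
- **Independent missingness may overstate the loss.** Clinical events tend to cost several scores in the same patient. At the extreme, with 5% of scores missing and all from the same patients, 5% of patients are lost rather than 14%. They then have no scores at all, and a mixed model recovers nothing.
- **The starting number is 72, not 66.** The 66 in the synopsis is already net of the dropout allowance, so deleting incomplete patients from it (giving 57 or 48) could count some losses twice.
- **A mixed model has limits.** It removes selection bias only if scores are missing at random, and a normal model is an approximation for a bounded 0-10 score, which is presumably why a rank option was included.

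The statistical analysis plan is not shown, and details such as covariance structure may properly sit there. The point here is different: the protocol itself names a method, and that method is a weak choice.

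**Conclusion.** The point holds for the overall across-day analysis of VAS. As written, that analysis either can delete patients with an incomplete set of scores or uses a rank procedure that is not identified and that, on its usual readings, gives no sound overall arm comparison on incomplete data.

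The size depends on assumptions. At 2% of scores missing the loss is small. At 5% to 10%, missing independently over three days, about 10 to 20 of 72 patients would be dropped (72 − 62 and 72 − 52), and fewer under clustering. The inflated type I error applies only if scores are pooled as independent.

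A reader might take section 10.1 to make VAS a co-primary endpoint and conclude that the trial's main result is at risk. The documents do not support that: the synopsis and section 3 list VAS as secondary, and the sample size rests on morphine use alone. The primary comparison and the sample size are untouched. The change is worth making because it is cheap, but it is not critical.

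**What to change.** Replace the pain-score sentence in section 10.3 with wording to this effect:

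- VAS at rest and VAS on coughing are each analysed with a linear mixed model for repeated measures, with arm, day and arm-by-day terms and an unstructured covariance.
- The model uses all observed scores from all randomised patients.
- The arm difference is reported with a 95% confidence interval, overall and by day.
- The per-day Mann-Whitney comparisons of the arms are kept as a sensitivity analysis for skewed or bounded scores, in place of ANOVA on ranks.

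The score times that enter the model should be listed, so that it is clear whether the 12-hour score is separate from day 1.

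The cost is wording only, with no new data, visits or patients. The covariance structure must be stated; unstructured means 3 × 4 / 2 = 6 parameters for three times, or 4 × 5 / 2 = 10 for four. The model relies on missing at random and approximate normality, and the report should say so.
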